3. STUDY OBJECTIVES

3.1. PRIMARY OBJECTIVE

The primary objective of the study is to compare the effect of piromelatine (5, 20, and 50 mg) to that of placebo in the change from baseline in global composite score of the computerized Neuropsychological Test Battery (cNTB) after 26 weeks of double-blind treatment.

The global composite score includes the computerized International Shopping List Test (ISLT; immediate and delayed recall), One Card Learning (OCL), Identification (IDN), Detection (DET), One Back Card (OBK), and the paper-based Controlled Oral Word Association Test (COWAT) and Category Fluency Test (CFT).

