3.2. SECONDARY OBJECTIVES

The key secondary objectives are:

1. To compare the effect of piromelatine (5, 20, and 50 mg) to that of placebo on global impression assessed by the Clinical Global Impression of Change (CGIC) after 26 weeks of double-blind treatment.
2. To compare the effect of piromelatine (5, 20, and 50 mg) to that of placebo in the Alzheimer's Disease Cooperative Study/Activities of Daily Living scale adapted for MCI patients (ADCS-MCI-ADL) at Weeks 13 and 26 and over 26 weeks of double-blind treatment.

The other secondary objectives are:

1. To compare the effect of piromelatine (5, 20, and 50 mg) to that of placebo in Alzheimer's Disease Assessment Scale cognitive subscale (ADAS-cog14) at Weeks 13 and 26 and over 26 weeks of double-blind treatment.
2. To compare the effect of piromelatine (5, 20, and 50 mg) to that of placebo in the change from baseline in global composite score of the cNTB at Weeks 4 and 13 and over 26 weeks of double-blind treatment.

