3.6. DETERMINATION OF SAMPLE SIZE

Eligible patients will be enrolled equally in a 1.2:1:1:1 randomization ratio to the 4 trial arms (placebo [1.2] and the equal piromelatine treatment arms 5 mg, 20 mg, and 50 mg [1:1:1]). Assuming an effect size between treatment dose and placebo of 0.35 over 26 weeks, a significant level (α) of 0.05 for one-sided test, and power of 80%, a sample size

of 115 patients for the placebo arm and 95 for each of the 3 piromelatine arms is calculated. Assuming a 50% screen failure rate and allowing for 15% patient withdrawal, 920 patients should be screened in order to randomly assign 460 patients, of whom it is expected 400 will complete the study. Enrollment will end on November 30th 2018.

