4. ENDPOINTS

4.1. PRIMARY EFFICACY ENDPOINT

The primary efficacy endpoint is the cNTB global composite score (ISLT immediate and delayed recall, OCL, IDN, DET, OBK, COWAT and CFT) over 26 weeks of double blind treatment.

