4.2. SECONDARY EFFICACY ENDPOINTS

Efficacy will be further assessed based on the following secondary variables:

- CGIC at Weeks 13 and 26 and over 26 weeks of double-blind treatment;
- ADCS-MCI-ADL at Weeks 13 and 26 and over 26 weeks of double blind treatment;
- ADAS-cog14 at Weeks 13 and 26 and over 26 weeks of double-blind treatment;
- cNTB global composite score (ISLT, ISLT-delayed, OCL, IDN, DET, OBK, COWAT, and CFT) over 4 and 13 weeks of double blind treatment.

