8. EFFICACY

8.1. PRIMARY EFFICACY ENDPOINT AND ANALYSIS

The primary efficacy endpoint is the change from baseline over 26 weeks of cNTB global composite score.

The global composite score of the cNTB is a composite score of the ISLT (immediate and delayed recall), OCL, IDN, DET, OBK and paper-based COWAT and CFT tests.

Calculation of scores: for each test listed above a z-score relative to study baseline will be calculated.

$$z - Score (z_{ijt}) = \frac{(x_{ijt} - \bar{x}_{1t})}{\sigma_{1t}} * Multiplicand$$

Where:

t = is the test indicator (ISLT, ISLT delayed, OCL, IDN, DET, OBK, COWAT or CFT)

i = indexes subject i

j = indexes the jth assessment for subject i (j = 1 means baseline)

x = cognitive score

x_{ijt} = subject's score for test t at the current assessment

\bar{x}_{1t} = mean performance score of the study sample for test t at baseline

σ_{1t} = standard deviation of the study sample for test t at baseline

Multiplicand equals 1 for tests for which a higher score is indicative of better cognitive performance (i.e., ISLT, ISLTR, OCL, COWAT, CFT) and -1 for tests where a lower score is indicative of better cognitive performance (i.e., IDN, DET, OBK)

Calculation of composite global score: A z-score for each test will be calculated as described above. A mean of all available z-scores for given patient in a given assessment will be calculated as the composite global score. For a given patient at a given assessment a minimum of 5 valid test scores of the tests listed above will be determined, of which at least 1 test are included from each of the domain composites as described in [Section 3.2](#).

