cNTB global composite scores and changes from baseline will be summarized (by treatment) at Visits 2, 3, 4 and 5. Change in cNTB global composite scores from baseline over 26 weeks (Visit 5) will be analyzed using a MMRM model utilizing all baseline and postbaseline data to assess any differences in treatment effects over time. The model will include fixed effects of treatment, study site, visit, and treatment by visit interaction, with baseline score, age, gender and ApoE4 as covariates, and a baseline by visit interaction. The global treatment effect estimates will be reported, with 95% confidence intervals and P values. Baseline will be the last non-missing observation at Visit 2 or before. The standard error of the change from baseline will also be included. The adjusted mean difference between treatments versus placebo will be presented along with the standard error and a 95% confidence interval.

These analyses will be performed by using PROC MIXED in SAS, and adjusted means will be obtained by using the LSMEANS statement.

An effect size calculation will be performed, where Cohen's d effect size will be calculated on the adjusted mean difference of change from baseline of treatment versus placebo. The effect size will be derived as the adjusted mean difference divided by the pooled standard deviation. The pooled within group variance (standard deviation squared) of two treatments is defined as:

$$\text{Pooled Variance} = [(n1 - 1)*\text{Var1} + (n2 - 1)*\text{Var2}] / (n1 + n2 - 2)$$

Where:

n1 = number of subjects with non-missing data for Placebo at Week 26

Var1 = variance for Placebo

n2 = number of subjects with non-missing data for active treatment at Week 26

Var2 = variance for active treatment

These analyses will be performed on the full analysis set and additionally on the per protocol set as a supportive analysis.

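### The SAP makes two different contrasts primary: change at Week 26 in Section 3.1, and change over 26 weeks (secondary in Section 3.2) in Sections 4.1 and 8.1

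*SAP*

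**What the plan says.** **Objectives.** The primary objective (Section 3.1) compares each dose with placebo on change in the "global composite score of the computerized Neuropsychological Test Battery (cNTB) after 26 weeks of double-blind treatment". The second of the other secondary objectives (Section 3.2) covers the "global composite score of the cNTB at Weeks 4 and 13 and over 26 weeks of double-blind treatment". In the objectives, then, the over-26-weeks effect is secondary and separate from the primary.

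**Endpoints.** Section 4.1 gives the primary endpoint as the composite (tests ending "OBK, COWAT and CFT) over 26 weeks of double blind treatment"). Section 4.2 lists the same score as secondary, ending "OBK, COWAT, and CFT) over 4 and 13 weeks of double blind treatment", with no 26-week item.

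**Analysis.** Section 8.1 repeats the Section 4.1 choice: "The primary efficacy endpoint is the change from baseline over 26 weeks of cNTB global composite score". It continues: "Change in cNTB global composite scores from baseline over 26 weeks (Visit 5) will be analyzed using a MMRM model". The model includes treatment, visit and their interaction. Then: "The global treatment effect estimates will be reported, with 95% confidence intervals and P values". No definition of the global effect, no visit weights and no LSMEANS contrast follow. The sentence on the adjusted mean difference against placebo names no visit.

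**Elsewhere.** Cohen's d in Section 8.1 uses patient counts at Week 26, the supportive ANCOVA uses change to Week 26, and the title of Table 14.2.1.2 says baseline to Week 26. The sample size (Section 3.6) is worded: "Assuming an effect size between treatment dose and placebo of 0.35 over 26 weeks". The primary-endpoint entry in Section 10 concerns only the added COWAT and CFT tests.

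**The concern.** An MMRM with a treatment-by-visit interaction produces several treatment comparisons. Two of them fit the SAP's wording of the primary: the difference at Visit 5, and the treatment effect averaged over Weeks 4, 13 and 26. These are different estimands. They have different true values unless the effect is constant over time, and different standard errors and power in any case.

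If the choice is still open when the data are unblinded, the same data under the same SAP could be reported as positive or negative. Choosing the more favourable contrast would also raise the false-positive rate. Neither problem can be repaired after unblinding, because the choice could no longer be shown to be independent of the results.

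**Working it through.** **1. The wording, side by side**

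| SAP section | Time frame for the cNTB global composite | Rank |
|---|---|---|
| 3.1 | after 26 weeks | primary |
| 3.2 | at Weeks 4 and 13, and over 26 weeks | other secondary |
| 4.1 | over 26 weeks | primary |
| 4.2 | over 4 and 13 weeks | secondary |
| 8.1, endpoint | over 26 weeks | primary |
| 8.1, MMRM | over 26 weeks, tagged Visit 5 | primary |
| 8.1, ANCOVA and Cohen's d | Week 26 | supportive / effect size |
| Table 14.2.1.2 | baseline to Week 26 | primary table |

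Reading *over* as *to Week 26* reconciles rows 1, 3 and 5–8. It fails for Section 3.2, where it would list the primary again as a secondary. It also fails for the other endpoints in Section 4.2 (CGIC, ADCS-MCI-ADL, ADAS-cog14), which are listed at Weeks 13 and 26 *and* over 26 weeks, so Week 26 would be named twice. Sections 3.3 and 4.3 use the same form. Reading *over* as a visit average fits those lists but conflicts with the Visit 5 tag, the Week 26 counts and the table title. Neither reading holds throughout.

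**2. The plan's own sample size**

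Inputs (Section 3.6): effect 0.35, one-sided α 0.05, power 80%, allocation 1.2:1.

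- Active arm: (1.645 + 0.842)² × (1 + 1/1.2) / 0.35² ≈ 92.5. Placebo: 1.2 × 92.5 ≈ 111, or 112 rounded up; 112/1.2 gives 94 per active arm. The SAP states 115 and 95, which is close.
- SE at 115 against 95 = √(1/115 + 1/95) = 0.1386 SD. Power = Φ(0.35/0.1386 − 1.645) = Φ(0.880) = 81.0%.

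This is one standardized difference, so it does not show which contrast was powered.

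**3. How far the two contrasts can differ**

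Assumptions, none given in the SAP: equal weights on Weeks 4, 13 and 26; equal visit variances; between-visit correlation ρ of change 0.5–0.7; Week 26 effect 0.35 SD; one-sided 0.05.

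- SD of the average relative to a single visit = √((1 + 2ρ)/3) = 0.816, 0.856, 0.894 for ρ = 0.5, 0.6, 0.7. This is also the correlation between the two test statistics.
- Linear growth: effects 0.35 × (4/26, 13/26, 1) = 0.054, 0.175, 0.350; mean 0.193.
- Constant: 0.35 at each visit.
- Power of the average = Φ(mean / (SD × 0.1386) − 1.645).

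| Profile | ρ | Power, Week 26 | Power, average | Exactly one significant |
|---|---|---|---|---|
| Linear | 0.5 | 0.810 | 0.524 | 0.305 |
| Linear | 0.6 | 0.810 | 0.492 | 0.326 |
| Linear | 0.7 | 0.810 | 0.465 | 0.348 |
| Constant | 0.5 | 0.810 | 0.926 | 0.138 |
| Constant | 0.6 | 0.810 | 0.904 | 0.122 |
| Constant | 0.7 | 0.810 | 0.881 | 0.104 |

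The last column comes from the bivariate normal distribution of the two statistics.

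**4. No treatment effect**

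The probability that at least one statistic exceeds 1.645 is 0.0742, 0.0716 and 0.0686 for ρ = 0.5, 0.6, 0.7, against 0.05 for a single named contrast.

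**5. Sensitivity**

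- Baseline-adjusted residuals, with equal correlation 0.5–0.8 among baseline and the three visits: the average has 54–59% power under linear growth and 94–96% under a constant effect. The direction is the same.
- Intermediate profile of 50%, 75% and 100% of the full effect, with the covariance of step 3: exactly one test is significant in about 15–16% of trials.

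**The case against.** The strongest reply is that *over 26 weeks* is loose wording for change to Week 26. Every part of Section 8.1 that names a visit for the primary points there: the Visit 5 tag, the Cohen's d counts and the ANCOVA outcome. The objective in Section 3.1 and the table title agree. For this same score, *over 4 and 13 weeks* in Section 4.2 plainly means change to those visits, as Section 8.2.4 confirms. The global-effect sentence is repeated for nearly every MMRM endpoint, including Section 8.2.4, where a 26-week average cannot be the target. That makes it weak evidence for an averaged primary.

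Much of this stands, and Week 26 is the better-supported reading. It does not settle the matter, because Sections 3.2, 3.3, 4.2 and 4.3 set the over-26-weeks effect beside named visits as a separate item. A sentence that is boilerplate still leaves the decisive P value without a defined contrast.

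Three further points stand as limits:

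- The table shells, attached to the SAP but not available here, may name the contrast. Section 10's silence is a fault only if the protocol's time frame differs, which cannot be checked.
- The power and disagreement figures depend on assumed trajectories and correlations. The 30–35% needs linear onset.
- One-sided 0.05 is stated for the sample size only; Section 8.1 gives 95% intervals and P values without naming a side. The error inflation also requires someone to choose after unblinding, and it is modest.

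**Conclusion.** The point holds, and the SAP is wrong as written: its objectives and its endpoint definitions give the same quantity different ranks, and the analysis section does not name the deciding contrast. That conclusion rests on the SAP's text alone and needs no assumption.

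The numbers show that the choice can matter. Depending on how the effect develops, the visit average can have much less or somewhat more power than the Week 26 contrast, and the two can return different answers in a material share of trials. Those figures are illustrations under the stated assumptions, not properties of this trial. The false-positive cost is small. The main harm is that the primary result is not uniquely determined, and this must be corrected before unblinding.

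**What to change.** Before unblinding, name one primary LSMEANS contrast against placebo. The Week 26 (Visit 5) treatment difference fits the primary objective and most of the operative text. If the visit average is intended, define the global treatment effect and state the visits and weights.

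Use the chosen wording in Sections 3.1, 3.2, 3.6, 4.1, 4.2 and 8.1, in the Cohen's d definition and in the title of Table 14.2.1.2. Label the other contrast secondary. Record the choice in Section 10 if it differs from the protocol.

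The cost is SAP wording, plus a check against the protocol's endpoint text and the table shells. The model, data and sample size do not change.

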5.3. FULL ANALYSIS SET

The full analysis set (FAS) will include all patients in the safety analysis set who have efficacy data for the primary parameter recorded for baseline and at least 1 post baseline assessment. Patients will be analyzed according to randomized treatment. The FAS will be used for all analyses of primary, secondary and exploratory efficacy endpoints (including the primary and secondary endpoints analysis of the combined 20 mg and 50 mg arm versus placebo) and for the summarization of demographics and baseline characteristics data.

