7.5. OTHER BASELINE CHARACTERISTICS

Duration of AD and severity of insomnia as expressed by PSQI score at baseline will be summarized by treatment group using the full analysis set.

Duration of AD will be calculated as:

$(\text{Date of informed consent} - \text{onset date of AD}) / 365.25$ and displayed to 1 decimal place.

For the calculation 01JAN will be imputed as only onset year of AD is recorded. Duration of AD and severity of disease will be summarized using summary statistics for continuous variables.

Duration of AD and severity of insomnia will be summarized using the full analysis set.

Optional ApoE4 genotyping will be summarized using the full analysis set. Subjects will be classified as ApoE4 carriers if they will have one or more copies of the ApoE4 allele. That is, subjects of the genotypes e4/e4, e4/e3 and e4/e2. Subjects without the ApoE e4 allele will be classified as Non-carriers (i.e., e3/e3, e3/e2, and e2/e2). This definition will be used for the subgroup exploratory analysis ([Section 8.3.11](#)).

Severity of insomnia will be determined using a score cutoff of ≥ 5 in PSQI global score for insomnia at baseline. This definition will be used for the subgroup analysis ([Section 8.3.12](#)).

Alzheimer disease medications at baseline will be summarized using the full analysis set. Subjects will be classified as naïve if they do not take acetylcholinesterase inhibitors and/or memantine at baseline. This definition will be used for the subgroup exploratory analysis ([Section 8.3.13](#)).

This will be summarized post data base lock (DBL) once the data is analyzed.

All data will be listed on the safety analysis set.

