A supportive efficacy analysis will be carried out using an ANCOVA method where the change in cNTB global composite scores from baseline to Week 26 will be the outcome variable and treatment group and study site will be main effects. cNTB global composite scores at baseline, age, gender, and ApoE4 will be included as covariates. The standard error of the change from baseline will also be included. Missing data (at the level of the composite score, not at the level of the individual tests) will be imputed using a pattern mixture model approach. Four patterns of missing data will be considered and imputed independently as follows:

- Pattern 1: will include patients who completed treatment on study drug (any missing data here is considered missing at random);
- Pattern 2: will include patients who discontinue treatment early due to adverse events (AEs);
- Pattern 3: will include patients who discontinue treatment early due to lack of therapeutic efficacy (LOTE);
- Pattern 4: will include patients who discontinue treatment early due to reasons other than AE event or LOTE.

The pattern mixture model methodology will be implemented using SAS procedures MI and MIANALYZE. Specifically, the following steps will be followed:

- Intermittent missing data will first be imputed using the Markov Chain Monte Carlo (MCMC) method implemented with the SAS MI procedure, which is appropriate for non-monotonic missing data.
- Data for patients who discontinue early will be multiply imputed as follows:
 - If the patient discontinues due to an AE (Pattern 2) or LOTE (Pattern 3), then missing data will be assumed to follow a distribution similar to the baseline values observed in the placebo arm of the study;
 - If the patient discontinues due to reasons other than an AE or LOTE (Pattern 4), at each time point, missing data will be assumed to follow a distribution similar to scores for patients that are still in the study and randomized to the same treatment group.
- Results of the ANCOVA on the multiply imputed data will be summarized using the SAS procedure MIANALYZE.

These analyses will be performed on the full analysis set and additionally on the per protocol set as a supportive analysis.

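### The primary model adjusts for optional ApoE4 genotype on the FAS, but no rule covers ungenotyped patients, so PROC MIXED run as written would drop them

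*SAP*

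**What the plan says.** **Models.** SAP 8.1 specifies the primary MMRM "with baseline score, age, gender and ApoE4 as covariates, and a baseline by visit interaction". On software it says "These analyses will be performed by using PROC MIXED in SAS", and on the analysis set "These analyses will be performed on the full analysis set and additionally on the per protocol set as a supportive analysis". For the supportive ANCOVA, "cNTB global composite scores at baseline, age, gender, and ApoE4 will be included as covariates", again on the FAS. Section 10 lists age, gender and ApoE4 as covariates among the changes from the protocol's analysis. Most secondary and exploratory models carry the same covariates.

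**Availability of ApoE4.** Section 7.5 begins "Optional ApoE4 genotyping will be summarized using the full analysis set", and 9.4 also calls the blood sample optional. Section 5.3 admits to the FAS patients in the safety set "who have efficacy data for the primary parameter recorded for baseline and at least 1 post baseline assessment"; a genotype is not required.

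**Coding.** Section 7.5 defines carriers as patients with at least one e4 allele, and for the rest says "Subjects without the ApoE e4 allele will be classified as Non-carriers", listing the three genotypes without e4. It adds "This definition will be used for the subgroup exploratory analysis". No class is defined for patients without a genotype.

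**Missing data.** Section 6.3 sets rules for missing baseline scores, ANCOVA outcomes, adverse event attributes and dates, and rules out any other imputation. Section 8.3.11 restricts the carrier-status subgroup analysis to patients who gave genetic consent. No such restriction, and no other rule, is attached to the primary model.

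**The concern.** A covariate that patients may decline is placed in the primary model, while the analysis set is defined without it. The SAP does not say what happens to an FAS patient who has no genotype. Under the software's default, that patient leaves the model, so the primary result would describe a subset selected by consent to genotyping while being labelled an FAS analysis.

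Two things are at stake. One is precision: the sample size in 3.6 makes no allowance for this loss, and section 10 records that planned power has already been cut from 88% to 80%. The other is prespecification: 9.4 has the ApoE4 data reported after database lock, and 3.7 places unblinding after database lock too. Without a written rule, who enters the primary model could be decided when treatment codes are available.

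**Working it through.** **Step 1: what happens to an ungenotyped FAS patient.**

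- The patient has baseline and post-baseline composite scores, so is in the FAS (5.3).
- ApoE4 is blank. The 7.5 classes rest on an observed genotype, and 6.3 bars imputing one.
- PROC MIXED omits any record with a missing fixed-effect covariate or class variable. ApoE4 does not vary by visit, so all of the patient's visits are omitted.
- The ANCOVA procedure is not named, but standard SAS linear-model procedures treat a missing covariate in the same way. The pattern mixture imputation in 8.1 fills in the composite score, not ApoE4, so it does not rescue these patients.

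**Step 2: reproduce the plan's power.** Inputs from 3.6: effect size d = 0.35, one-sided alpha 0.05, 115 placebo and 95 per active arm (115 + 3 × 95 = 400). For a two-sample t-test the noncentrality is d × √(n₁n₂/(n₁+n₂)) = 0.35 × √(115 × 95/210) = 2.524, with 208 df and critical value 1.652. Power is 0.808 (0.810 by the normal approximation), against 80% stated.

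**Step 3: drop the ungenotyped.** The SAP gives no rate, so 10%, 20% and 30% are assumed, equal in all arms. With genotyped fraction f, both arm sizes are multiplied by f. At f = 0.8 this gives 92 versus 76, noncentrality 2.258, 166 df and power 0.727. The four arms together contribute 400f = 400, 360, 320 and 280 patients.

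Two further assumptions are varied:

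- *Patients contributing.* Either the 400 evaluable, or all 460 randomised contributing fully (460 × 1.2/4.2 = 131.4 placebo, 460/4.2 = 109.5 per active arm), which is an upper bound on numbers.
- *Covariate gain.* If d is on the unadjusted SD and covariates explain a share R² of the variance, d becomes 0.35/√(1 − R²): 0.369 at R² = 0.10 and 0.391 at R² = 0.20.

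| Placebo vs active, R² | 0% ungenotyped | 10% | 20% | 30% | Ungenotyped share at which power is 80% |
|---|---|---|---|---|---|
| 115 vs 95, 0 | 0.808 | 0.771 | 0.727 | 0.676 | 2.3% |
| 131.4 vs 109.5, 0 | 0.854 | 0.819 | 0.778 | 0.729 | 15.0% |
| 115 vs 95, 0.10 | 0.843 | 0.808 | 0.766 | 0.716 | 12.0% |
| 131.4 vs 109.5, 0.10 | 0.885 | 0.854 | 0.815 | 0.768 | 23.4% |
| 115 vs 95, 0.20 | 0.879 | 0.847 | 0.808 | 0.760 | 21.7% |
| 131.4 vs 109.5, 0.20 | 0.915 | 0.888 | 0.853 | 0.809 | 31.8% |

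**Step 4: standard error.** This grows by 1/√f whatever the power assumptions: 1/√0.9 = 1.054, 1/√0.8 = 1.118, 1/√0.7 = 1.195.

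**Step 5: cost of keeping everyone.** A third ApoE4 level takes one degree of freedom. At 115 versus 95, power is 0.808 with either 208 or 207 df.

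These are two-sample approximations at one time point, not power for the repeated-measures model itself.

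**The case against.** The strongest reply is that the SAP writes no exclusion. Records drop only if the model variable is left blank, and the coding of ApoE4 as a model covariate is never stated, since the two-class definition is tied to the subgroup analysis. A not-genotyped level would therefore be compatible with the text. Some wording leans towards retention: the consent limit appears only in 8.3.11, and the table conventions in 12.2.5.2 call for an unknown or missing category. The coding might also be given in the table shells, which are attached but not shown.

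It is true that no exclusion is written and that a third level is permissible. But a permissible choice is not a specified one. Dropping these patients, adding a level and imputing can each give a different primary result, and the one that follows without further instruction is dropping. The 12.2.5.2 convention governs displays and does not define a covariate. What the shells contain cannot be checked here.

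A second reply is that the power figures show no harm, because the ungenotyped rate is unknown and the 80% crossing point moves from 2% to 32% with the assumptions. That stands as a limit on the size: no single threshold can be claimed. It does not remove the gap, which matters as soon as one FAS patient is ungenotyped.

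**Conclusion.** The concern holds and should be fixed. The SAP names the FAS for its primary analysis and specifies a model that, run as written, would use only genotyped FAS patients. The supportive ANCOVA has the same gap.

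The gap is clear from the text; its size is conditional on genotyping uptake. With equal loss across arms, the standard error rises by 5% to 20% over an assumed 10% to 30% ungenotyped. On the plan's own numbers without covariate gain, power per dose falls from 81% to between 77% and 68%. With full contribution from all 460 and covariates explaining 20% of the variance, it stays at 81% even at 30% ungenotyped. If nearly all patients are genotyped, the effect is negligible.

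No claim of bias is made. If consent to genotyping is unrelated to treatment, the cost is precision and a narrower population.

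**What to change.** In 8.1, and for every other MMRM or ANCOVA that adjusts for ApoE4 except the carrier-status subgroup analyses in 8.3.11, add:

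> ApoE4 is a class variable with three levels (carrier, non-carrier, not genotyped); no FAS patient is excluded from a model because ApoE4 is missing.

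The rule concerns ApoE4 only. A patient without a post-baseline value for an endpoint first measured at Week 13 still does not enter that endpoint's model. A separate level is not imputation, so 6.3 does not stand in the way.

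Report the number of patients at each ApoE4 level by arm. State also how LSMEANS weights the three levels: default equal weights would give the not-genotyped level one third of each arm's adjusted mean, whatever its frequency. Differences from placebo are unaffected, because the model has no treatment-by-ApoE4 term. Set the rule before treatment codes are released.

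The cost is SAP wording, one derived variable and one model degree of freedom. No new data are needed.
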